1. The proportion of patients with confirmed COVID-19 at the end of the period of preventive treatment of the drug (measurement period: 28 days).
2. The proportion of patients with acute respiratory viral infections, including COVID-19, at the end of the follow-up period (change period: 2 months).
3. The proportion of patients with confirmed COVID-19 at the end of the follow-up period (change period: 2 months).
4. Frequency of development of complicated course of ARVI.
5. The proportion of participants with each of the scores (0-8) according to the WHO Clinical Improvement Scale (change period: 28 days).
6. The proportion of participants with each of the scores (0-8) according to the WHO Clinical Improvement Scale (change period: 2 months).
7. Duration of symptoms of the disease of study participants who had acute respiratory viral infections, including COVID-19 (change period: 2 months).
8. The duration of the symptoms of the disease of the study participants who were infected with ARVI, including COVID-19 (measurement period: 28 days).

Confirmation of clinical cases of ARVI, including COVID-19:

In the following cases:

- 1) a positive result of PCR on SARS-CoV-2 RNA, regardless of the presence of clinical symptoms;
- 2) appearance of clinical symptoms of ARVI in the absence of a PCR result on SARS-CoV-2 RNA or in the case of a negative result on SARS-CoV-2 RNA, -

at any stage during participation in the study, a completion visit (Visit 3) is conducted at the end of the quarantine period (at least 14 days from the date of signing Consent for the treatment of a new COVID-19 coronavirus infection in outpatient settings (at home) and compliance with the isolation regime or discharge from the hospital in case of laboratory confirmation of COVID-19), at which the patient returns the participant's diary and reports his condition to the doctor-researcher, transmits information about hospitalization, duration of symptoms, results of tests and performed studies.

Definition of the COVID-19 case:

Suspicious case of COVID-19

Body temperature above 37.5° in addition to one or more of the following signs (in the absence of other known causes that explain the clinical picture, regardless of the epidemiological history):

- Cough (dry or with scant sputum)
- Shortness of breath
- Feeling of congestion in the chest
- SpO₂ no more than 95%
- Sore throat
- Nasal stuffiness or moderate rhinorrhea
- Smell disorders or anosmia
- Ageusia
- Conjunctivitis
- Fatigue

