In the case of ARVI symptoms characteristic of a suspicious case of COVID-19, accompanied by a negative result of PCR test, registered during or after a preventive course (during the period of participation in the study after randomization until the end of the observation period), the patient may additionally undergo a quantitative test for the presence of IgM and IgG antibodies to SARS-CoV-2 by the ELISA method for the purpose of additional verification and detection of COVID-19 cases. An additional quantitative test for antibodies to SARS-CoV-2 can be performed from the 10th to the 21st day after the appearance of the first symptom of ARVI to register the immune response of the acute phase of infection at the beginning of its development (increased IgM levels) or during high-grade response (increased IgM and IgG), considering the seronegative the period of the disease (5-7 days). The analysis is taken only in the absence of fever and a satisfactory general condition of the patient, accompanied by a favorable recovery dynamics. When interpreting the results, it is necessary to consider the probability of obtaining false positive results (for example, the presence of "cross-reacting" antibodies). If the interpretation of the results is difficult, it is allowed to conduct a repeated ELISA study using the same test systems after 5-7 days to assess the dynamics of indicators. Quantitative determination of IgM and IgG antibodies in the blood by the ELISA method will be carried out with the support of DiaLab LLC Plus."

The condition of the study participant is assessed according to the WHO standard scale of clinical improvement from 0 to 8 points at each visit, including a phone call visit. In case of registration of ARVI at the final visit 3, in parallel with the current assessment of the participant's condition, an additional assessment of the case is carried out according to the WHO scale, reflecting the maximum clinical manifestation of the disease.

WHO Clinical Improvement Scale

| Assessment on the WHO scale | 0 | 1 | 2 | 3 | 4 | 5 | 6 | 7 | 8 |
|--|---|--------------------------|-----------------------|---------------------------------|--|---|--|---|-------|
| Select the appropriate score from 0 to 8 | Not infected | Outpatient | | Hospitalized with mild form | | Hospitalized with severe form | | | Died |

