| | there are no clinical or virological signs of infection | no activity restrictions | activity restrictions | hospitalized, no oxygen therapy | hospitalized, oxygen therapy through a mask or nasal cannula | non-invasive lung ventilation or high-flow oxygen therapy | endotracheal intubation and mechanical ventilation | ventilation + additional organ support – pressor drugs, renal replacement therapy, extracorporeal membrane oxygenation (ECMO) | death |

Safety criteria

The assessment of the safety of treatment will be carried out based on registration of adverse events by analyzing complaints and subjective symptoms, comparative analysis of clinically significant changes in laboratory parameters, as well as the severity of these changes, using the CTCAE scale version 4.03 from 2010.

Each participant should be monitored by a researcher for the occurrence of adverse events, which should be classified according to the severity and connection with the drug under study during the entire period of participation in the study.

Adverse events:

Adverse reaction (AR) – an unintentional adverse reaction of the body associated with the use of a drug and suggesting the presence, at least, of a possible relationship with the use of a suspected medicinal product.

Adverse event (AE) – any adverse change in the state of health of the patient or the subject of a clinical trial to whom the drug (study) product was prescribed, regardless of the causal relationship with its use. AE may represent any adverse and unintended change (including deviation of the laboratory indicator from the norm), symptom or disease, the time of occurrence

of which does not exclude a causal relationship with the use of drug product, regardless of the presence or absence of a relationship with the use of drug product¹¹.

Symptoms of acute respiratory infection: fever, manifestations of general infectious intoxication, signs of respiratory damage are not considered as adverse event, however, they are recorded during the study and analyzed as data for evaluating effectiveness.

Assessment of the causal relationship:

Methods for assessing the degree of causal relationship are based on the following criteria:

- the presence of a reliable temporary association of the AE with the use of the study drug (AE are registered after the start of the use of the study drug before the completion of participation in the study);

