COVID-19 (total)	n/N (%)	n/N (%)
Of these: COVID-19 confirmed	n/N (%)	n/N (%)

COVID-19 probable	n/N (%)	n/N (%)
COVID-19 suspicious	n/N (%)	n/N (%)
p (between groups)		

Table 10. Results of the assessment of the incidence rate at the end of the study (ITT population, PP)

	GROUP I	GROUP II
Total subjects	N =	N =
ARVI	n/N (%)	n/N (%)
Not sick		
p (between groups)		

Table 11. Results of the assessment of the incidence of COVID-19 at the end of the study (ITT population, PP)

	GROUP I	GROUP II
Total subjects	N =	N =
COVID-19 (total)	n/N (%)	n/N (%)
Of these: COVID-19 confirmed	n/N (%)	n/N (%)
COVID-19 probable	n/N (%)	n/N (%)
COVID-19 suspicious	n/N (%)	n/N (%)
p (between groups)		

Table 12. Results of the assessment of the frequency of complicated course (ITT population, PP)

	GROUP I	GROUP II
Total subjects	N =	N =
Complications (total)	n/N (%)	n/N (%)
Of these: ...	n/N (%)	n/N (%)
...	n/N (%)	n/N (%)
p (between groups)		

Table 13. Results of evaluation of the frequency of different scores on the WHO scale at the end of the prevention period (ITT population, PP)

	GROUP I	GROUP II
Total subjects	N =	N =
0	n/N (%)	n/N (%)
1	n/N (%)	n/N (%)
2	n/N (%)	n/N (%)
3	n/N (%)	n/N (%)
4	n/N (%)	n/N (%)
5	n/N (%)	n/N (%)
6	n/N (%)	n/N (%)
7	n/N (%)	n/N (%)
8	n/N (%)	n/N (%)
p (between groups)		

Table 14. Results of evaluation of the frequency of different scores on the WHO scale at the end of the study (ITT population, PP)

Total subjects	GROUP I		GROUP II	
	N =	N =	N =	N =
0	n/N (%)		n/N (%)	
1	n/N (%)		n/N (%)	
2	n/N (%)		n/N (%)	
3	n/N (%)		n/N (%)	
4	n/N (%)		n/N (%)	
5	n/N (%)		n/N (%)	
6	n/N (%)		n/N (%)	
7	n/N (%)		n/N (%)	
8	n/N (%)		n/N (%)	
p (between groups)				

Table 15. Duration of symptoms of the disease (ITT population, PP)

Evaluation period	Parameter	GROUP I	GROUP II
At the end of the prevention period (28 days)	n		
	M		
	CO		
	min.		
	max.		
	Me		
At the end of the study (2 months)	n		
	M		
	CO		
	min.		
	max.		
	Me		
p (between groups)			

Table 16. Distribution of the nature of the symptoms of the disease (ITT population, PP)

Group	Symptom	Number of patients, percentage (%)
GROUP I		n/N (%)
GROUP II		n/N (%)
p (between groups)		

Table 17. Assessment of vital signs (safety population)

Visit	Group	Parameter	SBP (mmHg)	DBP (mmHg)	HR (beats/min)	RR (/min)	Temperature (°C)	Oxygenation (SpO ₂)
B0	GROUP I	n						
		M						
		CO						
		min.						
		max.						
		Me						
	GROUP II	N						
		M						
		CO						

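### WHO-scale endpoints 5 and 6 are tied to no defined score or ordinal test, and on the natural reading recovered cases count the same as never infected

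*Protocol*

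**What the plan says.** **Endpoints.** Secondary endpoint 5 (Protocol, Effectiveness criteria; SAP 3.1) reads "The proportion of participants with each of the scores (0-8) according to the WHO Clinical Improvement Scale (change period: 28 days". Endpoint 6 has the same wording for 2 months. Neither says whether the score is current or worst.

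**Scoring.** Under the COVID-19 case definitions, the protocol says the participant's condition "is assessed according to the WHO standard scale of clinical improvement from 0 to 8 points at each visit", the phone visit included. Score 0 means "there are no clinical or virological signs of infection". If ARVI is registered, then at Visit 3, alongside the current assessment, "an additional assessment of the case is carried out according to the WHO scale, reflecting the maximum clinical manifestation of the disease". Footnote 7 of the schedule of procedures and SAP 3.2 repeat this.

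**Timing.** Visit 2 is a phone call on Day 27 (±3) in the schedule, with no PCR. For ill participants "a completion visit (Visit 3) is conducted at the end of the quarantine period", meaning at least 14 days, or discharge from hospital. It can be delayed up to Day 90.

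**Analysis.** SAP 5.1 lists only endpoints 1 to 4 under secondary endpoint analysis. Table 13 covers the end of the prevention period. Table 14 is titled "Results of evaluation of the frequency of different scores on the WHO scale at the end of the study (ITT population, PP". Each has nine rows of counts (0 to 8) and one between-group p. The general rule in SAP 5.1 for categorical data is chi-squared, or Fisher's exact test if any expected count is below 5. No table shell shows the maximum score.

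**The concern.** The WHO scale is the plan's only graded measure of severity across all participants. If Tables 13 and 14 are filled with status on the visit date, someone hospitalised in week 2 and since recovered sits in the same row as someone never ill, and the gradation is lost.

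A nominal test then loses more: a shift from score 4 to score 1 carries no more weight than any other rearrangement of the rows.

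The gap also leaves a choice open. Every case seen at Visit 3 has two WHO scores, and the plan does not say which one feeds endpoint 6. In an open-label trial that choice should be fixed before the data are seen.

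**Working it through.** **Inputs.** Control incidence 5%, study incidence 2% (3 points lower) and 286 completers per group, from the protocol's Number of participants section. Visit 2 on Day 27, from the schedule. Illness duration is not given, so it is varied. Onset is assumed uniform over 27 days.

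**1. The plan's own figure.** The documents give no sample size or power for endpoints 5 and 6. The figure of 286 reproduces from the protocol's formula: (0.05 × 0.95 + 0.02 × 0.98) × 1.96² / 0.03² = 0.0671 × 3.8416 / 0.0009 = 286.4. Whether that formula is adequate is a separate matter.

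**2. Expected cases.** Control: 286 × 0.05 = 14.3. Study: 286 × 0.02 = 5.7.

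**3. Status at Visit 2.** With illness lasting D days, the share still ill is D/27 and the share back to 0 is 1 − D/27.

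| D (days) | Back to 0 | Non-zero, control | Non-zero, study |
|---|---|---|---|
| 3 | 89% | 1.6 | 0.6 |
| 5 | 81% | 2.6 | 1.1 |
| 7 | 74% | 3.7 | 1.5 |
| 10 | 63% | 5.3 | 2.1 |
| 14 | 48% | 7.4 | 3.0 |
| 21 | 22% | 11.1 | 4.4 |

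The share passes one half at D = 27/2 = 13.5 days. With exponential durations of mean m, the share still ill is (m/27)(1 − exp(−27/m)). That puts 82% back to 0 at m = 5 and 56% at m = 14.

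**4. Status at Visit 3.** No arithmetic is needed. The visit is timed to the end of quarantine or to discharge, so a current score of 3 to 7 arises only in someone still in hospital when the time limit forces a final assessment. Death (8) persists, and an infection first found by the Visit 3 PCR could score above 0. Most other cases should score 0.

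**5. Which test applies.** For all eight non-zero rows to reach an expected count of 5 in both arms would take 8 × 2 × 5 = 80 non-zero scores. At most 14.3 + 5.7 = 20 are expected. The default rule therefore leads to Fisher's exact test on a 2 × 9 table, which, like chi-squared, ignores order.

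**6. Illustrative power.** A simulation used 4,000 runs, 5% vs 2%, 286 per group, two-sided 0.05. The maximum-score mix among the ill was assumed: 45% score 1, 40% score 2, 7% score 3, 5% score 4, 1% each for 5 and 6, 0.5% each for 7 and 8. The nominal test was chi-squared over the occupied categories, not the Fisher branch. The ordinal test was Mann-Whitney.

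| Score used | Nominal | Ordinal |
|---|---|---|
| Visit status, 10% still ill | 0.00 | 0.04 |
| Visit status, 25% still ill | 0.03 | 0.14 |
| Visit status, 50% still ill | 0.08 | 0.25 |
| Maximum score | about 0.23 | about 0.50 |

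Both changes matter: the maximum score with a nominal test reaches only about 0.23.

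**The case against.** The best defence is that the documents never say endpoints 5 and 6 use visit status. Their wording refers to a period, and the SAP uses the same end-of-period phrasing for cumulative measures: incidence in Tables 8 to 11 and symptom duration in Table 15. The Visit 3 maximum belongs to the same assessment row of the schedule, so it may be what feeds Table 14. Nor is a nominal test prescribed: SAP 5.1 also offers Mann-Whitney for quantitative data. This stands to the extent that visit status and the nominal test are the natural readings, not explicit statements. It does not close the gap, since the plan still has to say which score and which test it means.

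A reader might also infer that most people who fell ill score 0 at Day 28. The documents do not support this: they give no illness duration, and above about 13.5 days it fails. Score 0 also requires no virological signs, no PCR is done at Visit 2, and the protocol's introduction says RNA can be found in sputum for a month. A symptom-free COVID-19 case is therefore not automatically 0.

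Nor is severity lost from the trial altogether. A recovered hospitalised participant still counts in the primary endpoint and in symptom duration, and in endpoint 4 if the course was complicated. The protocol also requires hospitalisation and death from ARVI complications to be recorded and analysed for effectiveness.

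Finally, an ordinal test on the maximum adds little pure severity information. Its simulated power of about 0.50 equals the calculated two-sided power for 5% vs 2% at 286 per group (0.50), so it largely re-tests ill against not ill. That is correct and limits what the fix can deliver.

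**Conclusion.** The point holds as an undefined score and an unspecified analysis. The natural reading makes endpoint 6 carry almost no information on severity and weakens endpoint 5 by an amount that depends on illness duration. At Visit 3 this follows from the visit's timing. At Visit 2 the share of cases back to 0 runs from 89% to 22% for illnesses of 3 to 21 days, assuming uniform onset. The power figures also depend on an assumed severity mix and are illustrative only.

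The stronger claim that both endpoints are uninformative by construction is not supported, because the documents do not state that visit status is used. These are two of eight secondary endpoints and the primary comparison is unaffected, but the correction is cheap and should be made.

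**What to change.** Define endpoints 5 and 6 as the worst WHO score from randomisation to Day 28 and to the end of follow-up, with 0 for participants never ill.

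- **2 months:** use the maximum already recorded at Visit 3.
- **Day 28:** this maximum is not available as described, because it is recorded only at Visit 3 and not dated. An illness starting on Day 24 and peaking on Day 31 would carry the wrong Day 28 value. Either ask for the worst score so far at the Visit 2 call, or date the maximum using the diary and the ARVI case form.
- **Analysis:** add endpoints 5 and 6 to the SAP's secondary analysis section with one pre-specified ordinal test (Wilcoxon or proportional odds). Retitle Tables 13 and 14 as worst score, and show visit status descriptively.
- **Severity among cases:** report it descriptively, since about 14 and 6 cases will not support a test.

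The cost is one added item at Visit 2 or a dated maximum, plus SAP wording and table titles. Visits and treatment do not change.

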This study will be conducted in accordance with the Research Program, the Helsinki Declaration (ICH Harmonized Tripartite Guideline for GCP) and current local regulatory requirements (GOST R 52379-2005 "Good Clinical Practice", Order of the Ministry of Health of the Russian Federation No. 200n dated 01.04.2016 "On approval of the rules of good clinical practice"), The Rules of Good Clinical Practice of the Eurasian Economic Union (approved by the Decision of the Council of the Eurasian Economic Commission No. 79 of November 03, 2016), as well as according to the principles of the Independent Ethical Committee (IEC) accompanying this study. The research protocol, informed consent, participant diaries and the list of researchers must be submitted to the IEC before the start of the study and the inclusion of the first participant.

Informed consent

Each potential participant of the study will be informed about the study drug, objectives, and essence of the study, expected benefits, degree of risk and the requirements that he/she must fulfill during the study.

The participant's information sheet with the informed consent form will be signed and dated by both the volunteer and the researcher in two copies. One copy is transferred to the participant, and the other remains in the file of the research center. Each volunteer will receive information about the study in writing on hand. Information about the study is presented in Russian.

Risks and benefits for the study participant

The study drug has a low degree of toxicity and possible efficacy in relation to the prevention of COVID-19. All information that will be provided to the volunteer to decide on participation, including information about potential risks, is indicated in the participant's information sheet with an informed consent form.

Possible risks

The following side effects have been registered for the injectable dosage form of the drug (lyophilizate for the preparation of solution for intramuscular and subcutaneous administration). The appearance of these effects during intranasal administration of the drug Ingaron® is not expected.

It is noted that the use of the drug Ingaron® may be accompanied by the development of side effects, represented mainly by manifestations of flu-like syndrome: fever, chills, headache,

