muscle pain, joint pain, weakness, which develop after the first injections of the drug and are amenable to correction with drugs with antipyretic and analgesic effects, without requiring withdrawal of the drug. In most cases, fever did not rise above 37.5 °C and was controlled independently.

Basically, registered side effects were reversible and easily controlled by the appointment of concomitant therapy (antidepressants for depression; antiallergic agents for skin rash): thrombocytopenia^{2*}, neutropenia^{3*}, anemia^{2*}, lymphopenia⁴; autoimmune thyroiditis, allergic reactions⁵; vomiting^{2*}, nausea²; weight loss, anorexia³; depression; general malaise, headaches³, dizziness; rhinorrhea; allergic rash, alopecia^{6**}; myalgia³; increased concentration of liver enzymes^{3**}, increased concentration of bilirubin^{3*}, creatinine^{3*}, urea^{3*}, glucose^{3**}.

Risks from the use of the studied drug Ingaron® for the course of pregnancy, fetal development or for a breastfed child has not been sufficiently studied. In this regard, pregnant and lactating women, as well as women capable of childbearing and unwilling to follow reliable methods of contraception, as indicated in the inclusion/non-inclusion criteria, are not allowed to participate in this study. If a case of a participant's pregnancy is detected during the study, she is excluded from the study ahead of schedule and is subject to medical supervision during the entire period of pregnancy, as well as within 6 months after the birth period to assess the condition of the woman and the born child (observation is carried out if possible and only if she has her desire and consent to such observation).

Risk/benefit ratio

Considering the above, as well as the satisfactory study of the drug Ingaron® for intranasal administration when used in clinical practice, including for preventive purposes, the risk/benefit ratio in this study can be considered acceptable.

Benefit

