Any additional information and supporting documentation (blinded copies of the results of laboratory tests, procedures, pathologist's report or postmortem epicrisis in case of death, etc.) will be provided by the Researcher in additional written messages of LLC NPP Pharmaclon. In case of death of a participant, the Researcher is obliged to provide any additional information at the request of LLC NPP Pharmaclon.

The initial report (completed form of notification of AR) and subsequent detailed and additional reports should identify the subjects of the study by the unique numbers assigned to them, not by the names of the subjects or their addresses and other personal data.

In connection with the occurrence of serious adverse events, the researcher is obliged to notify the ethics committee. The Ethics Committee may, if necessary, discontinue or cancel the study.

The minimum information that should be included in the initial notification of the occurrence of an urgently reported event should contain the identification data of the participant under which he passes in the study, identification data of the person reporting the occurrence of this phenomenon (full name of the chief researcher or authorized employee), characteristics of the event that occurred and its causal relationship with the use of the investigated drug.

Except those cases when the urgently reported event was sufficiently documented in the initial message about its occurrence, the researcher must provide all additional information available to him in subsequent messages about the urgently reported event using the same form, the same ways of its transmission and the time frame as established for the initial message about the urgently reported event. These procedures should continue until AE has been fully documented and reported.

After sending by e-mail the completed SAE notification, researcher must place the originals of the initial and subsequent messages about urgently reported events in investigator file.

Events deemed NOT to require urgent notification include:

- hospitalization for optional or pre-planned treatment of concomitant diseases that the participant had prior to inclusion in the study, the course of which did not worsen during participation in the study;
- hospitalization, death, or life threatening due to the development of complications of ARVI (COVID-19) – however, this information is necessarily recorded and analyzed to assess effectiveness.

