4.2. Registration, analysis, and evaluation of safety parameters

Adverse events were recorded from the moment of signing the informed consent until the end of the study. The safety analysis of the drug will consider the data of physical examination, diaries of participants, laboratory tests or other assessments. The study will analyze the frequency of occurrence and the nature of AE and SAE. The safety assessment was carried out throughout the study.

Adverse event (AE)

Adverse event (AE) – any adverse change in the state of health of the patient or the subject of a clinical trial to whom the drug (study) product was prescribed, regardless of the causal relationship with its use. AE may represent any adverse and unintended change (including deviation of the laboratory indicator from the norm), symptom or disease, the time of occurrence of which does not exclude a causal relationship with the use of drug product, regardless of the presence or absence of a relationship with the use of drug product¹.

Symptoms of acute respiratory infection: fever, manifestations of general infectious intoxication, signs of respiratory damage are not considered as adverse event, however, they are recorded during the study and analyzed as data for evaluating effectiveness.

Adverse reaction (AR)

Adverse reaction (AR) – an unintentional adverse reaction of the body associated with the use of a drug and suggesting the presence, at least, of a possible relationship with the use of a suspected medicinal product.

Determination of a serious adverse event (SAE)

Serious adverse event (SAE) – AE that leads to death², poses a threat to life³, requires hospitalization of the patient or its prolongation⁴, leads to persistent or severe uncapacity or disability, to congenital anomalies or malformations⁵, requires medical intervention to prevent the development of these conditions.

¹ Due to statistical necessity, adverse events are recorded both in the study group and in the control group. Evaluation and registration of adverse events begins from the moment of signing the informed consent form.

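### Infection-type symptoms are kept out of adverse events without proof of infection, so flu-like or nasal reactions may be missing from the AE tables and counted as ARVI

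*Protocol*

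**What the plan says.** **The exclusion.** The protocol (Safety criteria, Adverse events) states: "Symptoms of acute respiratory infection: fever, manifestations of general infectious intoxication, signs of respiratory damage are not considered as adverse event". It continues: "however, they are recorded during the study and analyzed as data for evaluating effectiveness". SAP 4.2 carries the same rule: "signs of respiratory damage are not considered as adverse event, however, they are recorded during the study and analyzed as data for evaluating effectiveness".

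**The listed reactions.** The protocol's Possible risks section opens with "The following side effects have been registered for the injectable dosage form of the drug" and says these effects are not expected with intranasal use. The list is led by "manifestations of flu-like syndrome: fever, chills, headache", followed by muscle pain, joint pain and weakness. A second list includes "dizziness; rhinorrhea; allergic rash".

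**The ARVI case rule.** The protocol (Confirmation of clinical cases of ARVI) and SAP 3.2 register a case in two ways. One is a positive SARS-CoV-2 PCR. The other is ARVI symptoms with PCR negative or not available.

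**Serious outcomes.** Protocol footnote 12 and SAP footnote 2 say that a death from COVID-19 is noted in the medical record without SAE registration. The protocol's Urgent event section exempts hospitalisation, death or threat to life from ARVI complications from urgent notification, and says the information is still analysed for effectiveness.

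**The concern.** Safety is the protocol's stated secondary objective. The symptoms left out of AE reporting overlap heavily with the only reactions the protocol lists for this drug. The rule depends on a symptom being one of acute respiratory infection, yet neither document says how to decide that when no virus has been found. An investigator who follows the text can record a drug-related fever or runny nose as ARVI and make no AE entry.

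Two things are at stake. A low AE count for these symptoms in Group I could reflect good tolerability or merely the recording rule, and the report could not tell them apart. The same classification also feeds the primary endpoint, where few events are expected.

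**Working it through.** No figure in the plan states the size of this problem, so the main check is textual.

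**1. Does the exclusion require infection to be shown?** No. It names symptoms of acute respiratory infection but sets no laboratory or clinical test for infection.

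**2. Can a symptom alone become an ARVI case?** Yes. A negative or missing PCR is enough, and the ARVI rule sets no symptom count or temperature threshold. The 37.5 °C threshold belongs to the suspicious and probable COVID-19 definitions. Most fevers with the injectable form did not exceed 37.5 °C, so they would usually miss those definitions but could still count as ARVI.

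**3. Do the symptoms overlap?** Fever, headache, myalgia and rhinorrhea appear both in the injectable-form reactions and in the COVID-19 sign list. Weakness is close to the fatigue in that list.

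**4. Do other SAP tables fill the gap?**

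| Table | Content | Why it does not repair this |
|---|---|---|
| 18–23 | AEs and SAEs, safety population | Contain only events registered as such |
| 17 | Temperature, respiratory rate, SpO₂ and other vital signs, safety population | Visits 0 and 3 only. Visit 3 is due on Day 56–62, at least 56 − 27 = 29 days after the 27-day course, though a registered ARVI can move it |
| 16 | Symptoms by group, ITT and PP | Presented as symptoms of the disease, with no link to dosing |
| 13–14 | WHO scores 0–8, including hospitalised and died, ITT and PP | Efficacy tables |
| 12 | Complicated course, ITT and PP | Efficacy table |

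Visit 2, at the end of dosing, is a phone call without physical examination. The Group I diary gives the clock time of each instillation but only start and end dates for complaints.

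**5. What could it do to the primary endpoint?** This is an illustration with assumed rates. The design rates are 5% and 2%: (0.05 × 0.95 + 0.02 × 0.98) × 1.96² / 0.03² = 286.4, which reproduces the plan's 286 per group. About 315 × 0.02 = 6.3 true cases are then expected in Group I. Suppose a fraction r of Group I has a reaction, all reactions are booked as ARVI, and the control rate stays at 5%. The Group I rate becomes 0.02 + 0.98r.

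| Assumed r | Reactions, 315 × r | Group I rate | Two-sided power, 315 per arm |
|---|---|---|---|
| 0 | 0 | 2.0% | 53.5% |
| 0.5% | 1.6 | 2.5% | 38.2% |
| 1% | 3.1 | 3.0% | 25.3% |
| 2% | 6.3 | 4.0% | 9.2% |

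For each r this is the worst case in one direction, because no reaction is recognised as such. It shows only that the endpoint is sensitive to a handful of misclassified people. It is not an estimate.

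**The case against.** Keeping endpoint symptoms out of AE counts is a declared and common choice in prevention trials, and the symptoms are recorded and tabulated by arm. Several stronger readings that a reader might draw do not stand.

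- **That these symptoms can never be AEs.** The rule covers symptoms of acute respiratory infection only. The AE definition is broad, the causality criteria foresee an AE during instillation, and intolerance to the drug is an exclusion criterion. A symptom judged non-infectious can be registered. The protocol also refers to a separate Guide on Adverse Events, which is not among the documents and may hold the missing criterion.
- **That these are known or likely reactions to the nose drops.** The list is for the injectable form, and the flu-like effects are said to follow the first injections. The documents list no local nasal reactions.
- **That the safety tables cannot show them at all.** Table 17 includes temperature, respiratory rate and SpO₂. The safety set is the ITT set analysed by actual treatment, so Table 16 covers nearly the same people.
- **That ARVI hospitalisations are struck from the SAE tables.** The urgent-event exception concerns notification. Explicit exemption from SAE registration is given only for COVID-19 deaths.
- **That the primary endpoint is biased against the drug by a known amount.** No intranasal reaction rate is given. In an open-label trial an investigator could also dismiss a true Group I infection as a reaction, which would favour the drug.

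What remains is that the protocol and SAP give no criterion for separating reaction from infection, and the other tables do not link symptoms to dosing.

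**Conclusion.** The point holds as a gap in safety reporting. Followed as written, the plan allows reactions of the kind listed for the injectable form to be absent from Tables 18–23 and counted as ARVI. The AE tables therefore cannot test the statement that such effects are not expected intranasally.

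COVID-19 deaths are outside SAE registration. The tables that lay out ARVI hospitalisation and death by arm are the WHO-scale efficacy Tables 13–14, and whether ARVI hospitalisations also enter the SAE counts is not stated. No safety table gives all hospitalisations and deaths by arm.

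The effect on the primary endpoint cannot be sized or signed from the documents, and the illustration rests wholly on its assumed rates. The conclusion also assumes that the separate adverse event guide does not already set the criterion. The change is worth making because it is cheap and serves a stated objective. The documents do not show that any harm has been hidden.

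**What to change.** 1. In the protocol and SAP 4.2, limit the AE exclusion to laboratory-confirmed infection. If the adverse event guide already has a criterion, bring it into both documents.
2. When PCR is negative or not done, keep the ARVI record and also log the symptoms on the AE form, in both arms. In Group I, add the interval since the last instillation. The protocol already prefers this interval, in hours, for AE records. Site staff must ask for it, because the diary gives only complaint dates.
3. Add one SAP table, safety population by arm, of fever, flu-like and nasal symptoms, and of all hospitalisations and deaths regardless of attribution. Cross-refer to Tables 12–14 and 16.

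**Cost.** Revised wording, more AE records and one table. PCR is planned only for SARS-CoV-2, so many ordinary colds will be logged twice, and the new table will overlap with Tables 12–14 and 16.

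**Limit.** This repairs safety reporting. It leaves the primary endpoint definition unchanged, so a reaction booked as ARVI still counts as a case.
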